#### 3.2.1.2 Exclusion Criteria

- 1. Imminent delivery planned (within 3 weeks of enrollment) as sequencing results would not be available prior to delivery
- 2. Prenatal sequencing or planned prenatal sequencing performed outside of the study. Gene panels may be performed prior to enrollment but the results must be known and negative to be eligible (positive or unknown results are an exclusion).

- 3. Maternal or paternal age less than 18 years old
- 4. Proven infectious, teratogenic, or other genetic cause of fetal anomaly
- 5. For twin gestation, anomalies in both fetuses (NT, IUGR, or structural anomaly)
- 6. Monochorionic diamniotic (MCDA) and monochorionic monoamniotic (MCMA) twins as well as higher-order multifetal gestations
- 7. Planned termination of the fetus or intrauterine fetal demise (IUFD)
- 8. Unavailable blood or saliva samples from both genetic parents prior to sequencing
- 9. Parental unwillingness to participate in 1 year postnatal follow-up
- 10. Language barrier (non-English or Spanish speaking)
- 11. Previous consent to the unsequenced prenatal group or enrollment in a previous pregnancy

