# 3.2.2 Prospective unsequenced prenatal group

#### 3.2.2.1 Inclusion Criteria

- 1. Fetus identified by ultrasound and/or MRI with at least one of the following:
  - a. One or more suspected major structural anomalies (Appendix A)
  - b. A nuchal translucency measurement of  $\geq$  3.5 mm and < 4.5 mm without evidence of cystic hygroma
  - c. A fetus less than 24 weeks 0 days gestation with normal anatomy and sonographically estimated fetal weight <5th %ile without maternal hypertension, type I diabetes, or other maternal disorders known to alter fetal growth
- 2. Declined prenatal sequencing
- 3. Singleton gestation or dichorionic diamniotic (DCDA) twin gestation.
- 4. Gestational age less than 36 weeks, 0 days

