#### 3.2.2.2 Exclusion Criteria

- 1. Prenatal or postnatal (prior to neonatal discharge) CMA with pathogenic or likely pathogenic variants that are related to the prenatal ultrasound finding
- 2. Maternal or paternal age less than 18 years old
- 3. Proven infectious, teratogenic, or other genetic cause of fetal anomaly
- 4. Positive prenatal NIPT screening for trisomy 21, 18 or 13. Positive 22q11.2 prenatal NIPT testing with consistent ultrasound findings is also an exclusion.
- 5. For twin gestation, anomalies in both fetuses (NT, IUGR, or structural anomaly)
- 6. Monochorionic diamniotic (MCDA) and monochorionic monoamniotic (MCMA) twins as well as higher-order multifetal gestations.
- 7. Planned termination of the fetus or intrauterine fetal demise (IUFD)
- 8. Unable to consent both genetic parents
- 9. Parental unwillingness to participate in 1 year postnatal follow-up

10. Language barrier (non-English or Spanish speaking)

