#### 3.2.3.1 Inclusion Criteria

- 1. Fetus identified by ultrasound and/or MRI with at least one of the following:
  - a. One or more suspected major structural anomalies (Appendix A)
  - b. A nuchal translucency measurement of  $\geq$  3.5 mm and < 4.5 mm without evidence of cystic hygroma
  - c. A fetus less than 24 weeks 0 days gestation with normal anatomy and sonographically estimated fetal weight <5th %ile without maternal hypertension, type I diabetes, or other maternal disorders known to alter fetal growth
- 2. Did not pursue prenatal sequencing
- 3. Singleton gestation or dichorionic diamniotic (DCDA) twin gestation.
- 4. Gestational age less than 36 weeks, 0 days at date study-specified anomalies first diagnosed

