#### 3.2.3.2 Exclusion Criteria

- 1. Prenatal or postnatal (prior to neonatal discharge) CMA with pathogenic or likely pathogenic variants that are related to the prenatal ultrasound finding
- 2. Maternal or paternal age less than 18 years old
- 3. Proven infectious, teratogenic, or other genetic cause of fetal anomaly
- 4. Positive prenatal NIPT screening for trisomy 21, 18 or 13. Positive 22q11.2 prenatal NIPT testing with consistent ultrasound findings is also an exclusion.
- 5. For twin gestation, anomalies in both fetuses (NT, IUGR, or structural anomaly)
- 6. Monochorionic diamniotic (MCDA) and monochorionic monoamniotic (MCMA) twins as well as higher-order multifetal gestations.
- 7. Termination of the fetus or intrauterine fetal demise (IUFD) within 3 weeks of date of initial anomaly diagnosis
- 8. Language barrier (non-English or Spanish speaking)
- 9. Delivery at a site other than one of the study centers or associated hospitals
- 10. Unable to access prenatal or neonatal records

[figure not shown]

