# 4 Study Procedures

# 4.1 Screening for Eligibility and Consent

Eligible patients with specified fetal structural anomalies will be identified by prenatal ultrasound and/or fetal MRI. Center investigators and their staff in the outpatient ultrasound prenatal diagnostic units will be responsible for identifying eligible patients. To maximize recruitment, coordinators at each center will screen the prenatal diagnostic logs on a daily basis to identify eligible patients.

Upon recognition of a specified fetal anomaly, the maternal fetal medicine physician (MFM)/ ultrasonographer and/or a genetic counselor will explain the ultrasound finding as per routine clinical care. At the conclusion of the initial evaluation/consult, women will be informed by the physician/counselor and/or coordinator about the study. Once the potential participant indicates willingness to hear more about the study, a study coordinator will meet with the parents, review eligibility, and explain the study. Women who choose to undergo prenatal invasive testing will be approached for the prenatal sequencing group but will not be enrolled until a negative or non-causal karyotype/CMA is confirmed (with the exception of those enrolled into expedited prenatal sequencing, section 4.2.1). Women who choose not to have any diagnostic testing or decline sequencing will be approached for participation in the unsequenced prenatal group. A portion of the unsequenced group will be enrolled through medical record review under a waiver of consent. All women with a specified fetal anomaly will be recorded on a screening log that collects screening ID, date screened, planned invasive prenatal testing, ultrasound anomaly, screening status code and reason for study ineligibility (if applicable). A participant flowchart is shown in Figure 1.

Figure 1. Prospective screening flowchart

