#### 4.2.3 Retrospective unsequenced prenatal group

The retrospective unsequenced prenatal group will include participants from the screening log who did not actively decline enrollment and are otherwise eligible. Participants will be considered enrolled at the time of diagnosis of the fetal anomaly.

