## 5.3 Prenatal Sequencing and Prenatal Unsequenced Groups

Clinical management including health care utilization and cost, and pregnancy and neonatal outcomes will be compared among the prenatal sequencing group and the unsequenced prenatal group (prospective and retrospective). Women whose fetus or neonate is found to have pathogenic or likely pathogenic causal findings on CMA prior to neonatal discharge will be excluded from these analyses. Twelve month postpartum outcomes will be compared only among those individuals enrolled prospectively. Initially, demographic data and severity of ultrasound findings will be compared to ensure there are no significant differences between the two study groups (prenatal sequencing and unsequenced prenatal group). If differences are found, the covariates will be adjusted for in the analyses.

Categorical variables will be reported as the number and frequency and associations assessed by the Pearson's chi-square or Fisher's Exact test. The distributions for continuous variables will be assessed for normality and transformed to fit a normal distribution if possible. Normal distributions will be reported as mean and standard deviation and compared with the t-test, and non-normal data will be reported as median and interquartile range and compared with the Mann-Whitney U test.

For each outcome, if the study groups show a significant difference, interactions will be tested and subgroup analyses conducted if the interaction is significant (p<0.05). Pre-specified subgroup analyses include maternal age, race/ethnicity, fetal sex, and type of anomaly (lethal vs non-lethal).

The amount of missing data, missing data patterns, and identification of variables associated with missingness will be explored to inform the primary and sensitivity statistical analyses. Analytic techniques used to address missing data bias will be used as appropriate. A two-sided nominal p-value less than 0.05 will indicate statistical significance.

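### Planned delivery within 3 weeks is an exclusion for the sequenced group only, so these pregnancies can enter the charge and perinatal comparison only as controls; the size of the bias, and its direction on charges, are unknown

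*Combined protocol and SAP*

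**What the plan says.** All references are to protocol version 1.8.

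- Section 3.2.1.2, exclusion 1, sequenced group: "Imminent delivery planned (within 3 weeks of enrollment) as sequencing results would not be available prior to delivery".
- Sections 3.2.2.1 and 3.2.2.2, prospective controls: they must have declined sequencing and meet "Gestational age less than 36 weeks, 0 days". The nearest exclusion is "Planned termination of the fetus or intrauterine fetal demise (IUFD"), which does not cover a planned live delivery.
- Sections 3.2.3.1 and 3.2.3.2, retrospective controls: they must not have pursued prenatal sequencing and must meet "Gestational age less than 36 weeks, 0 days at date study-specified anomalies first diagnosed". This list does use a 3-week window, but only here: "Termination of the fetus or intrauterine fetal demise (IUFD) within 3 weeks of date of initial anomaly diagnosis".
- Section 4.2.3: retrospective controls are "participants from the screening log who did not actively decline enrollment and are otherwise eligible", counted as enrolled on the date of anomaly diagnosis.
- Section 4.1: the screening log holds "screening status code and reason for study ineligibility (if applicable").
- Section 5.3: utilization, cost, and pregnancy and neonatal outcomes are "compared among the prenatal sequencing group and the unsequenced prenatal group (prospective and retrospective"). Covariates are adjusted for if the groups differ on demographics or ultrasound severity. Neither the delivery plan nor gestational age at entry is named.

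**The concern.** Aim 2 asks what having sequencing results before birth does to management and cost. A pregnancy due to be delivered before results could arrive cannot inform that question. The plan recognizes this for the sequenced group but keeps the same pregnancies as comparators.

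The affected outcomes are the second primary outcome (maternal and neonatal hospital charges) and the secondary outcomes measured during the delivery stay: gestational age at delivery, major morbidities, initial NICU stay and death by discharge. A difference on any of these could come partly from who was allowed into each group.

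The omission also sits oddly with the amendment history. The June 2020 amendment added this exclusion to the sequenced group alone, while changing other control criteria expressly to align them with that group.

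**Working it through.** **Can such a woman enter each group?**

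- *Sequenced:* no, by exclusion 1.
- *Retrospective control:* yes. If she was screened out of sequencing for imminent delivery, she is on the log, did not actively decline and did not pursue sequencing. She qualifies if her anomaly was first diagnosed before 36w0d and no other exclusion applies.
- *Prospective control:* a narrower route. She must have declined sequencing, so a woman barred from it may not qualify. A woman who does decline is not screened for imminent delivery.

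**Is this only a difference in start date?** No. Under section 4.2.2, women who have invasive testing but decline sequencing enroll after a negative karyotype/CMA, as standard-path sequenced women do under 4.2.1. The exclusion still applies to one side only.

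**How early are these deliveries?** Entry can be as late as 35w6d, so delivery within 3 weeks can be as late as 38w6d. It is certain to be preterm only for entry before 34w0d (33w6d + 3 weeks = 36w6d).

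**The plan's power figure.** Section 5.1 gives lognormal charges with mean $277,902 and SD $389,484, 500 vs 300 participants, ratio 0.80, two-sided alpha 0.05 and 80% power.

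- CV = 389,484 / 277,902 = 1.4015
- Log-scale variance = ln(1 + 1.4015²) = 1.087; SD = 1.042
- SE of the log ratio = 1.042 × √(1/500 + 1/300) = 0.0761
- |ln 0.80| / SE = 0.2231 / 0.0761 = 2.93; power = Φ(2.93 − 1.96) = 83.4%

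With Mann-Whitney efficiency 3/π the figure is 81.7%. The stated 80% is close and slightly conservative; nothing below depends on it.

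**Illustrative bias with no true effect.** Both f (share of the 300 controls) and R (their charge ratio to other controls) are assumptions.

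- Apparent geometric-mean ratio, sequenced/control = exp(−f ln R)
- Apparent arithmetic-mean ratio = 1 / (1 + f(R − 1))
- Control log-variance = 1.087 + f(1 − f)(ln R)²; two-sided error by normal approximation

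| f | R | Geometric ratio | Arithmetic ratio | Two-sided error |
|---|---|---|---|---|
| 2% | 2 | 0.99 | 0.98 | 5.4% |
| 3% | 2 | 0.98 | 0.97 | 6% |
| 5% | 3 | 0.95 | 0.91 | 11% |
| 10% | 3 | 0.90 | 0.83 | 29% |
| 5% | 0.5 | 1.035 | 1.03 | 7.4% |

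The last row's error equals that for f=5%, R=2, because only the sign of ln R changes.

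**Power after removing a share f of controls** (log-scale test, ratio 0.80): 5% (285 left), 82.2%; 10% (270), 80.9%; 15% (255), 79.4%. With Mann-Whitney efficiency the 10% figure is 79.1%.

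**The case against.** The exclusion has a sound practical reason: results would arrive too late. That justifies it for the sequenced group but does not explain keeping the same pregnancies as controls.

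The stronger objections concern direction and size, and most of them stand.

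- *Direction on charges.* A reader might infer that the imbalance makes sequencing look cheaper. The documents do not support that. Neonatal charges stop at discharge or death (4.10.1), and Appendix A admits lethal anomalies such as anencephaly and renal agenesis. A planned early delivery followed by early death could cost less than an average control, which would bias against sequencing.
- *Preterm delivery.* A reader might also infer that most of these deliveries are preterm. No frequency is given, and entry from 34w0d can lead to delivery at term.
- *Share.* Only planned deliveries are covered; unplanned early delivery can occur in every group. Growth-only cases must be under 24 weeks and isolated nuchal translucency is a separate category, so late-diagnosed structural anomalies are the likely source. The share may be small.
- *Spread.* The log-scale SD comes from deliveries with a NICU admission at one center. If the cohort's spread is wider, the error rates above are too high for the same f and R.
- *Adjustment.* Section 5.3 adjusts for ultrasound severity if the groups differ and names a lethal/non-lethal subgroup. Either might absorb part of the effect, but neither is a delivery plan. Gestational age at delivery is itself an outcome, so adjusting for it would not be a clean remedy.
- *Scope.* The 12-month outcomes are collected only on prospectively enrolled participants, so the retrospective route cannot affect them.

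**Conclusion.** The one-sided rule is in the current text and no other section closes it. The retrospective group is the main opening. The bias probably favours sequencing on gestational age at delivery. Its direction on charges is not established, and its size is unknown because f and R are not in the documents. Over the assumed values the apparent geometric-mean charge ratio runs from 0.90 to 1.035 against a design effect of 0.80; at f of 2% to 3% with R=2 it is negligible. This is an inexpensive alignment worth making, not a demonstrated threat to the charge comparison.

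**What to change.** 1. Add the planned-imminent-delivery exclusion to sections 3.2.2.2 and 3.2.3.2.
2. In 4.2.3, exclude women whose screening-log reason for sequencing ineligibility was imminent delivery.
3. In 5.3, apply the same restriction to controls already enrolled.
4. Judge it from the delivery plan charted at the index date, or from the log reason, not from the actual delivery date. Unplanned early deliveries then stay in all groups and the restriction does not select on an outcome.
5. Count the 3 weeks from a comparable index date. Counting from each group's own enrollment would leave a gap, because retrospective controls start at diagnosis and standard-path sequenced women start after CMA. For controls without a CMA, one option is diagnosis plus the typical diagnosis-to-CMA-result interval seen in the sequenced group, with a sensitivity analysis that varies this date.

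The cost is some chart abstraction, since section 4.3 lists no delivery plan among baseline items; some misclassification where no plan was charted; and the loss of a few controls, who may or may not be replaceable from the log. At a 10% loss, power for a ratio of 0.80 is about 81% on the log-scale test.

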# 3.2.2 Prospective unsequenced prenatal group

#### 3.2.2.1 Inclusion Criteria

- 1. Fetus identified by ultrasound and/or MRI with at least one of the following:
  - a. One or more suspected major structural anomalies (Appendix A)
  - b. A nuchal translucency measurement of  $\geq$  3.5 mm and < 4.5 mm without evidence of cystic hygroma
  - c. A fetus less than 24 weeks 0 days gestation with normal anatomy and sonographically estimated fetal weight <5th %ile without maternal hypertension, type I diabetes, or other maternal disorders known to alter fetal growth
- 2. Declined prenatal sequencing
- 3. Singleton gestation or dichorionic diamniotic (DCDA) twin gestation.
- 4. Gestational age less than 36 weeks, 0 days

#### 3.2.2.2 Exclusion Criteria

- 1. Prenatal or postnatal (prior to neonatal discharge) CMA with pathogenic or likely pathogenic variants that are related to the prenatal ultrasound finding
- 2. Maternal or paternal age less than 18 years old
- 3. Proven infectious, teratogenic, or other genetic cause of fetal anomaly
- 4. Positive prenatal NIPT screening for trisomy 21, 18 or 13. Positive 22q11.2 prenatal NIPT testing with consistent ultrasound findings is also an exclusion.
- 5. For twin gestation, anomalies in both fetuses (NT, IUGR, or structural anomaly)
- 6. Monochorionic diamniotic (MCDA) and monochorionic monoamniotic (MCMA) twins as well as higher-order multifetal gestations.
- 7. Planned termination of the fetus or intrauterine fetal demise (IUFD)
- 8. Unable to consent both genetic parents
- 9. Parental unwillingness to participate in 1 year postnatal follow-up

10. Language barrier (non-English or Spanish speaking)

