# 2 Background

#### 2.1 Introduction

With advances in prenatal imaging, increasingly there is the ability to detect birth defects prenatally and use this information to optimize perinatal and neonatal management. Simultaneously, molecular genetic diagnostics have facilitated more precise identification of the underlying cause of these birth defects and provided additional prognostic information to improve prenatal and postnatal management. The first major improvement in prenatal genomic diagnosis was chromosome microarray analysis (CMA) which identifies copy number variants (CNVs) of 100 kb to 10Mb that are below the resolution of most karyotypes. A multicenter study evaluating the clinical utility of prenatal CMA reported that CMA identified the same aneuploidies and unbalanced rearrangements as karyotyping but also identified additional, clinically significant cytogenetic information. Among women with a normal karyotype, CMA identified clinically relevant deletions or duplications in 6.0% with a fetal structural anomaly and in 1.7% of those with indications of advanced maternal age or positive aneuploidy screening results. The frequency of CNVs varied by anomaly, with the highest frequency (16%) occurring in fetuses with cardiac defects.

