# 3.2 Eligibility Criteria

#### 3.2.1 Prenatal sequencing group

#### 3.2.1.1 Inclusion Criteria

- 1. Fetus identified by ultrasound and/or MRI with at least one of the following:
  - a. One or more suspected major structural anomalies (Appendix A)
  - b. A nuchal translucency measurement of  $\geq$  3.5 mm and < 4.5 mm without evidence of cystic hygroma
  - c. A fetus less than 24 weeks 0 days gestation with normal anatomy and sonographically estimated fetal weight <5th %ile without maternal hypertension, type I diabetes, or other maternal disorders known to alter fetal growth.
- 2. Negative prenatal CMA (or those with CMA findings not related to the ultrasound finding)
- 3. Singleton gestation or dichorionic diamniotic (DCDA) twin gestation.
- 4. Gestational age less than 36 weeks, 0 days to allow for availability of sequencing results before delivery

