#### 4.2.2 Unsequenced prenatal group

The prospective unsequenced prenatal group will include participants that decline invasive testing and those that plan to have invasive testing but decline sequencing (Figure 1). For participants that plan to have invasive testing but decline sequencing, enrollment into the study will occur after the clinical karyotype/CMA results are confirmed negative and the participant signs the prenatal unsequenced consent. Participants that decline invasive testing will be enrolled at the time of diagnosis of the fetal anomaly and they sign the unsequenced prenatal group consent. Women from this group who later elect invasive testing are not eligible to enroll in the prenatal sequencing group but will be included in the unsequenced prenatal analyses if the karyotype and CMA are confirmed negative or non-causal.

Postpartum genetic testing (karyotype and CMA) and genomic sequencing may be performed at the discretion of the clinical care team as part of routine care. Continued follow-up of the pregnancy and 1-year postpartum period will not take place if a pathogenic or likely pathogenic causal CMA is identified prior to neonatal discharge.

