#### 9.2 Recruitment and Data Collection Period

Educational materials will be developed targeted to participants and referring physicians.

There are 1,800 pregnancies/year with structural anomalies eligible for enrollment in the study at the participating centers. Assuming that 40% of these will undergo diagnostic testing, and 25% will have an abnormal karyotype or CMA, and 50% of those eligible will consent to sequencing, it is estimated that

approximately 270 patients per year or 23 patients will be enrolled per month, with overall recruitment of 750 patients completed in ~33 months. The 350 controls would be recruited within the same time period. If recruitment falls below targets, additional sites may be added.

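### A negative or non-causal prenatal CMA is required of every sequenced pregnancy but not of all controls, so the charge and perinatal comparisons can be biased in either direction.

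*Combined protocol and SAP*

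**What the plan says.** The two groups enter under different chromosomal rules (protocol version 1.8).

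- **Sequenced group.** Section 3.2.1.1 makes this an inclusion criterion: "Negative prenatal CMA (or those with CMA findings not related to the ultrasound finding". Under the expedited pathway in Section 4.2.1, a pregnancy whose CMA proves pathogenic or likely pathogenic and presumed causal leaves the analysis.
- **Prospective controls.** Section 3.2.2.1 has no CMA criterion. Section 3.2.2.2 excludes "Prenatal or postnatal (prior to neonatal discharge) CMA with pathogenic or likely pathogenic variants that are related to the prenatal ultrasound finding". Section 4.2.2 sets this rule for women who accept an invasive procedure and refuse only the sequencing: "enrollment into the study will occur after the clinical karyotype/CMA results are confirmed negative and the participant signs the prenatal unsequenced consent". By contrast, "Participants that decline invasive testing will be enrolled at the time of diagnosis of the fetal anomaly". After birth, "Postpartum genetic testing (karyotype and CMA) and genomic sequencing may be performed at the discretion of the clinical care team".
- **Retrospective controls.** Section 3.2.3.2 repeats the CMA exclusion, and Section 3.2.3.1 has no CMA criterion.
- **Other removals in both control groups.** These are a positive NIPT for trisomy 21, 18 or 13, a positive 22q11.2 result with matching ultrasound findings, and any other proven genetic cause.
- **Analysis.** Section 5.3 pools prospective and retrospective controls for charges and perinatal outcomes. "Women whose fetus or neonate is found to have pathogenic or likely pathogenic causal findings on CMA prior to neonatal discharge will be excluded". Adjustment is planned for demographic and ultrasound-severity differences, if found. CMA status is not named, and no analysis is limited to CMA-negative controls.

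**The concern.** A fetus with a causal abnormality that CMA would detect cannot be in the analysed sequenced group. The same fetus can stay in the control group if nobody tested it, or if the CMA result came after neonatal discharge. The main objective in Section 1.2 concerns pregnancies with a negative or only non-causal karyotype/CMA, and untested controls are not known to belong to that population.

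The second primary outcome (maternal and neonatal hospital charges) and the perinatal outcomes are therefore compared between a screened group and a partly screened one. Part of any difference could reflect chromosomal disease rather than sequencing. Adjusting for demographics and ultrasound severity cannot be relied on to remove the effect of a diagnosis that was never made. The 15% control loss in Section 5.1 allows for causal CMA results that are found, or delivery elsewhere. It does not allow for disease that is not found.

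**Working it through.** **Inputs**

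- Section 5.1: approximately lognormal charges, mean $277,902, SD $389,484; 500 sequenced and 300 controls; two-sided alpha 0.05; 80% power for a mean ratio of 0.80.
- Section 9.2: 1,800 eligible pregnancies a year, 40% having diagnostic testing, "25% will have an abnormal karyotype or CMA", and half of those eligible consenting to sequencing.
- Section 2.1: "CMA identified clinically relevant deletions or duplications in 6.0% with a fetal structural anomaly" among women with a normal karyotype; also an abnormal CMA in 5–10% of fetal anomalies.
- Not in the documents, so assumed: the share of controls never tested, the fraction *p* of analysed controls with undetected causal disease, and the ratio *R* of their charges to those of other controls.

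**1. The plan's own power figure**

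- CV = 389,484 / 277,902 = 1.4015
- Log-SD = √ln(1 + 1.4015²) = 1.042
- SE of the log ratio = 1.042 × √(1/500 + 1/300) = 0.0761
- Power for 0.80 = Φ(0.2231/0.0761 − 1.96) = Φ(0.97) = 83.4%

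The stated 80% is slightly conservative. Nothing below depends on the gap.

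**2. A gross range for *p***

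Section 9.2 leaves 60% of eligible pregnancies untested. If that share held among controls, 60% × 5% = 3%, 60% × 10% = 6% and 60% × 25% = 15%. The share among controls could be higher. Each year there are 1,800 × 0.60 = 1,080 untested pregnancies, and 1,800 × 0.40 × 0.75 × 0.50 = 270 tested, negative and not sequenced. Sampling controls in proportion would give 1,080/1,350 = 80% untested. The actual mix is not stated, so 40–80% is used below. All these values of *p* are before removals for NIPT, proven genetic cause or a pre-discharge CMA.

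**3. Effect on the charge comparison when sequencing does nothing**

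The control log-mean shifts by *p* ln *R*, with log-SD taken as unchanged.

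- Ratio, sequenced to control, log scale = *R*^(−*p*)
- Ratio of arithmetic means = 1/(1 + *p*(*R* − 1))
- Two-sided rejection = Φ(−1.96 + |*p* ln *R*|/0.0761) + Φ(−1.96 − |*p* ln *R*|/0.0761)

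| *p* | *R* | Ratio, log scale | Ratio, arithmetic | Rejection (nominal 5%) |
|---|---|---|---|---|
| 2% | 2 | 0.99 | 0.98 | 5.4% |
| 6% | 2 | 0.96 | 0.94 | 8.5% |
| 10% | 2 | 0.93 | 0.91 | 15% |
| 6% | 0.5 | 1.04 | 1.03 | 8.5% |
| 10% | 0.5 | 1.07 | 1.05 | 15% |

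Rows with *R* = 2 show an apparent saving. Rows with *R* = 0.5 show an apparent excess, which would hide a real saving.

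**4. What a restricted comparison could detect**

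If 40–80% of 300 controls are untested, 180 to 60 remain.

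- 180 controls: SE = 1.042 × √(1/500 + 1/180) = 0.0906; power for 0.80 = Φ(2.46 − 1.96) = 69%
- 60 controls: SE = 1.042 × √(1/500 + 1/60) = 0.1424; power for 0.80 = Φ(1.57 − 1.96) = 35%

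**The case against.** The controls are not wholly unscreened. Prospective controls who have invasive testing must be confirmed negative, and the NIPT and proven-cause exclusions remove further cases. Keeping untested controls was deliberate: the amendment history for 15 June 2020 explains that not all infants will have a postnatal CMA. Aim 2 asks what happens with and without prenatal sequencing, and the first primary outcome, diagnostic yield, is untouched. Table 2 collects clinical genetic results for controls, so some diagnoses will be known.

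All of this stands, and it narrows the problem. It does not close it. Each safeguard acts only on what was tested and found, and Section 5.3 makes no use of CMA status beyond the pre-discharge exclusion.

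A reader might go further and infer that sequencing will be credited with a false saving. The documents do not support a direction. They give no charges by chromosomal status, and Section 4.10.1 ends neonatal charges at discharge or death, so early death can lower them. If sicker infants are the ones tested before discharge, those left undetected need not be the costly ones.

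A reader might also take 60% × 25% = 15% as the affected share and, with doubled charges, reach a ratio of 0.90 and 28% false positives. The arithmetic is right, but the 25% applies to women who had diagnostic testing, counts karyotype and CMA together, and comes before every removal. It is an upper bound for that untested share, not an expected value.

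**Conclusion.** The imbalance is in the current text and bears on a primary outcome. Following the plan exactly can leave undetected causal disease of the kind CMA finds among controls only. The charge and perinatal comparisons can then be biased towards a false saving or towards a masked one.

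Neither the size nor the sign can be settled from the documents. At 2% affected with doubled charges the effect is negligible. At 6% to 10% affected the apparent saving is about 4% to 7% on the log scale, against the 20% reduction the study is sized for, and the false-positive rate is about 8.5% to 15%. These figures assume no true effect, the plan's log-SD of 1.04 with 500 against 300, unchanged spread, and a twofold charge ratio with no source in the documents. They show that the issue deserves a planned analysis. They do not predict the result.

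**What to change.** Amend Section 5.3 as follows.

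1. Keep the all-controls comparison as primary.
2. Report CMA/karyotype status by group: prenatal negative or non-causal, postnatal negative, never tested.
3. Prespecify a sensitivity analysis of charges and perinatal outcomes limited to controls with a negative or non-causal prenatal karyotype/CMA, which matches the sequenced group's condition. Controls tested only after birth should not be added, because that testing is selective.
4. Add a quantitative bias analysis that varies the share of untested controls with a causal abnormality, and their relative charges both above and below 1.
5. Interpret the charge difference in light of items 2 to 4, with no formal requirement that the analyses agree. With roughly 35–69% power for a ratio of 0.80, chance alone could make them differ.

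The cost is SAP wording and some extra analysis. Section 4.3 and Table 2 already provide for karyotype, CMA and other genetic reports on controls, so no new data collection is needed. The restricted control set is smaller (about 60–180 of 300 under the 40–80% assumption). It is also a selected group: women who had invasive testing but were not sequenced. It can support the primary comparison but not replace it.
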